5.5.12 Laboratory

Safety laboratory samples are centrally analyzed by ACM and the results are electronically transferred to Actelion. In exceptional cases, the protocol allows the utilization of local laboratories. Local laboratory analysis results are entered in the eCRF with some exceptions for blinding reasons (e.g., lymphocytes are not entered in the eCRF, see protocol). Quantitative results from local laboratories are not summarized (i.e. not included in summary statistics or graphical representations). Qualitative results like (marked) abnormality categorization, liver test elevation categories, etc. are derived from local laboratory data and summarized together with qualitative results derived from central laboratory data.

Safety laboratory hematology, clinical chemistry and urinalysis comprise the following parameters planned as per protocol:

Hematology: Red blood cell count, Total and differential WBC counts (basophils, eosinophils, lymphocytes, monocytes, neutrophils, band forms), Platelet count, Hemoglobin, Hematocrit.

Liver function tests and coagulation: INR, ALT, AST, AP, total bilirubin.

Clinical chemistry (excl. liver tests): Lactate dehydrogenase, Creatinine, creatinine clearance (calculated by the central laboratory using Cockcroft-Gault), Blood Urea Nitrogen, Urate, Glucose, Total cholesterol, Triglycerides, Sodium, potassium, chloride, calcium, Total protein, albumin, C-reactive protein

Urinalysis (dipstick provided by central laboratory): pH (5.0, 6.0, 6.5, 7.0, 7.5, 8.0, 8.5), Glucose (Negative, Trace, +, ++, +++, +++++), Proteins (Negative, Trace, +, ++, +++, +++++), Occult Blood (Negative, Trace, +, ++, +__), Leukocytes (Negative, Trace, +, ++, +__), Bilirubin (Negative, +, ++, +__), Urobilinogen (3.2, 16, 33, 66, ≥ 131). Also, for each of those parameters it is collected whether the result is normal or abnormal, and - if abnormal - whether clinically significant (no/yes).

For the above protocol planned parameters for hematology, liver tests, and clinical chemistry, the derivations detailed in Section 5.5.12.1 will be performed.

Derivations (other than treatment day of assessment) are not performed for any other laboratory parameters, and only the raw information and treatment day of assessment are

listed. This includes any laboratory parameters that were not planned to be collected per the protocol, and the following protocol planned parameters:

Hepatitis B Virus Surface Antigen, Varicella Zoster Virus IgG Antibody, HIV-1/2 Antibody, Hepatitis C Virus Antibody, M. tuberculosis IFN Gamma Response, pregnancy tests (Choriogonadotropin Beta, serum / urine), Teriflunomide plasma concentration.

5.5.12.1 Derivations

Numerical results are converted into both conventional and SI units as per QS document OTH-000005 (Definition of Marked Abnormalities in Laboratory Data). Results reported as below the lower limit of quantification (LLOQ) are set to the LLOQ value. Results reported as $> XX$ are set to XX for calculation of summary statistics. For all quantitative safety laboratory data, baseline, last on-treatment, Day-15 follow-up, Day-30 follow-up, last follow-up assessment is flagged and absolute change from baseline and percent changes from baseline are calculated for each post-baseline value, as described in Section 5.5.1.

Flags are derived according to project specific ranges for marked laboratory abnormalities as documented in the protocol [see Appendix D]. Marked laboratory abnormalities are labeled to indicate the increasing severity of abnormally low (“LL”, “LLL”), or high values (“HH”, and “HHH”) for each of the laboratory parameter listed. For INR, the general range specified in the protocol is applied to all subjects irrespective of concomitant treatment with anticoagulants.

The following flags will be derived for Alanine aminotransferase (ALT), Aspartate aminotransferase (AST), Total bilirubin (TBIL), and Alkaline phosphatase (ALP):

- ALT: $\geq 1 \times \text{ULN}$, $\geq 3 \times \text{ULN}$, $\geq 5 \times \text{ULN}$, $\geq 8 \times \text{ULN}$, $\geq 10 \times \text{ULN}$, $\geq 20 \times \text{ULN}$
- AST: $\geq 1 \times \text{ULN}$, $\geq 3 \times \text{ULN}$, $\geq 5 \times \text{ULN}$, $\geq 8 \times \text{ULN}$, $\geq 10 \times \text{ULN}$, $\geq 20 \times \text{ULN}$
- ALT or AST: $\geq 3 \times \text{ULN}$, $\geq 5 \times \text{ULN}$, $\geq 8 \times \text{ULN}$, $\geq 10 \times \text{ULN}$, $\geq 20 \times \text{ULN}$
- TBIL $\geq 2 \times \text{ULN}$
- ALT or AST $\geq 3 \times \text{ULN}$ and TBIL $\geq 2 \times \text{ULN}$ (at the same sample date)
- ALT or AST $\geq 3 \times \text{ULN}$ and TBIL $\geq 2 \times \text{ULN} + \text{AP} < 2 \times \text{ULN}$ (at the same sample date)
- INR > 1.5 combined with ALT or AST $\geq 3 \text{ ULN}$ (at the same sample date).

5.5.13 Other safety variables

5.5.13.1 Pulmonary function tests - Spirometry

Spirometry measurement data are collected using vendor machines from ERT. Data is automatically submitted to ERT by the machine. Prior to database lock and unblinding, Spirometry data are not transferred to any member of Actelion biostatistics as these data

are considered to carry a moderate risk of potential unblinding. The following parameters are provided:

- Forced Vital Capacity [FEV1] (L),
- Forced Expiratory Volume in 1 Second [FVC] (L),
- FEV1/FVC (%),
- Predicted FEV1 (L),
- Percent Predicted FEV1 [%FEV1] (%),
- Predicted FVC (L),
- Percent Predicted Forced Vital Capacity [%FVC] (%),
- Peak Expiratory Flow (L/s),
- Forced Expiratory Flow 25–75% (L/s),
- Forced Expiratory Flow 25% (L/s),
- Forced Expiratory Flow 50% (L/s),
- Forced Expiratory Flow 75% (L/s)

Several efforts per visit per subject may be recorded in the database (usually 8 efforts), and potentially even two or more sets of efforts per subject per visit (e.g., 2×8 efforts). For each set of efforts the best effort at a visit per parameter (e.g., FEV1, FVC) is identified by the spirometry over read at ERT (variable XPSPID = "0"). The central reader grades the best effort as 'acceptable', 'borderline', or 'unacceptable' (variable 'BTR Grade Code').

Analyses are based on best efforts. If two or more sets of efforts are available at the same visit the following algorithm applies for the selection of the effort at that visit. Only one best effort per subject per visit will be selected. FEV1/FVC (%) is rederived from the FEV1 best effort and FVC best efforts. The selection of the records is defined as follows:

Step 1: Only select 'best effort' records.

Step 2:

- a. If at least one 'acceptable' or 'borderline' rated test is available at a visit, chose the highest parameter value amongst all available 'acceptable' or 'borderline' rated test at that visit (per parameter).
- b. If no 'acceptable' or 'borderline' rated test is available, but at least one 'unacceptable' rated test is available, chose the highest parameter value amongst all available 'unacceptable' rated tests at that visit (per parameter).

Note: if only one value is present at a visit then this is the highest value and it is selected.

Step 3:

For baseline choose the highest value prior to study treatment start.

Note: For deriving baseline apply the algorithm from above on all available records that could qualify for baseline (e.g., if two sets of efforts are available on two different days prior to study treatment start, derive BL as the highest best effort).

Note: To favor selection of re-screening records for re-screened subjects, records qualifying for baseline are selected in a two-step approach: (i) Derive baseline based on all records collected in a 45-day window prior to study treatment start. If no such record is available, then (ii) derive baseline based on all records prior to study treatment start.

Baseline is flagged and absolute and percent changes from baseline are calculated for each post-baseline value, and last on-treatment and follow-up assessments are derived as described in Section 5.5.1.

Assessments meeting the following conditions are flagged in the ADaM dataset:

- Percent change from baseline in FEV1: $< -20\%$, $< -30\%$
- Percent change from baseline in FVC: $< -20\%$, $< -30\%$
- Absolute change from baseline in %FEV1: $< -20\%$, $< -30\%$
- Absolute change from baseline in %FVC: $< -20\%$, $< -30\%$
- FEV1/FVC $< 70\%$
- Absolute change from baseline in FEV1 ≤ -200 mL or percent change from baseline in FEV1 $\leq -12\%$
- Absolute change from baseline in FVC ≤ -200 mL or percent change from baseline in FVC $\leq -12\%$
- Absolute change from baseline in FEV1 > -200 mL and percent change from baseline in FEV1 $> -12\%$
- Absolute change from baseline in FVC > -200 mL and percent change from baseline in FVC $> -12\%$

In the subset of subjects experiencing a decrease of ≥ 200 mL or $\geq 12\%$ in FEV1 (or FVC) from baseline to the last assessment on treatment, the condition is considered **Reversible**, if no decrease of ≥ 200 mL and $\geq 12\%$ in FEV1 (or FVC) from baseline is present at the last follow-up assessment. If the last follow-up assessment is not fulfilling the above described reversibility criteria, the condition is considered **Not reversible**. If no follow-up assessment is available, reversibility cannot be assessed due to missing data.

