4.3 Clarifications concerning endpoint definitions and related variables or statistical methods

The protocol endpoints 'Change from baseline to EOS vs change from baseline to EOT' for lymphocyte counts, pulmonary function tests (PFTs) and DL_{CO} parameters analyses for assessing reversibility are clarified as follows: 'Change from baseline to EOS' is clarified to not include assessments from the post-treatment observation period, but only from the safety follow-up period (up to EOT + 37 days). Consequently, in this SAP the terminology 'change from baseline to last follow-up assessment' instead of 'change from baseline to EOS' is used. The rationale for this is to allow the assessment of the reversibility of the effects on these endpoints prior to the initiation of other DMTs in the PTOP.

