5.5 Safety variables

5.5.1 Definition of treatment-emergency, baseline and change-from-baseline, last on treatment, follow-up assessments for safety variables

For all safety data analyses described in this SAP, baseline is considered to be the last valid assessment prior to first study drug intake.

For each individual safety variable, baseline is defined to be the last valid measurement available before the date and time of first dose intake of study treatment, unless otherwise specified. On days where study drug is initiated or re-initiated, the pre-dose assessment for that day is defined as the last non-missing assessment prior to the study drug intake on that day. The pre-dose assessment on Day 1 (if available) is identical to baseline; however, missing pre-dose data on Day 1 is not imputed with baseline. In case of (partially) missing assessment dates/times, or for assessments reported on Day 1 (or day of re-initiation) with recorded assessment time contradicting the time point label (e.g., pre-dose, 2 hours post-dose), the nominal visit and time point labels will be used to determine whether an assessment is considered for baseline (for example a blood pressure measurement with an assessment date on Day 1 but with a missing assessment time or an assessment time prior to the reported time of first study drug intake, will not be considered for baseline if reported under the time-point “2 hours post-dose” in the eCRF, however it will be considered if reported as “Pre-dose” in the eCRF).

Absolute changes from baseline are defined as post-baseline value minus baseline value, i.e., a positive sign indicates an increase compared to baseline.

A percentage change from baseline is defined as the absolute change from baseline divided by the baseline value (if the baseline value is > 0) and then multiplied by 100.

Absolute and percent change from baseline is calculated and stored for all continuous safety data.

In addition, the following assessments are flagged or derived per parameter:

- Last on-treatment assessment: Last assessment prior to or on EOT date +1 day)
- Day-15 follow-up, between EOT + 8 days and EOT + 22 days [see Section 11.4]
- Day-30 follow-up, between EOT + 23 days and EOT + 37 days [see Section 11.4]
- Last follow-up assessment: Last assessment between EOT + 8 and EOT + 37 days

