9.10.6 Pulmonary function tests - Spirometry

The following summary displays are provided by treatment group, all based on the SAF:

- Treatment-emergent FEV1, FVC, FEV1/FVC, %FEV1, and %FVC including absolute and percent change from baseline, as described in Section 5.5.13.1, are summarized, by parameter and visit. Except for 'Baseline', 'Last on treatment', 'Day-15 follow-up' and 'Day-30 follow-up', only treatment-emergent results from nominal scheduled visits are included; premature EOT visit is mapped to a scheduled visit [see Section 11.3]. These are summarized descriptively and mean changes from baseline are also presented graphically with their standard error over time (plots starting with zero change at baseline).
- A scatter plot of all measured treatment-emergent %FEV1 values is provided. Treatment groups are color-coded and linear regression lines (with time as explanatory variable) are drawn per treatment group. These regression lines are to visualize the course over time after an initial change in pulmonary function and for that reason, exclude measurements taken prior to study day 26. The regression equation is given in a footnote.
- Number and percentage of subjects with any occasion of treatment-emergent low spirometry values as defined in Section 5.5.13.1 are presented. Percentages are based on the number of subjects with at least one treatment-emergent result available for the corresponding parameter;

- In the subset of subjects experiencing a decrease of ≥ 200 mL or $\geq 12\%$ in FEV1 (or FVC) from baseline to the last assessment on treatment, the number and percentage of subjects with the condition reversed, not reversed, or missing data on reversibility at the last follow-up result is provided;
- FEV1, FVC, FEV1/FVC, %FEV1, %FVC at the following three time points (for definition, see Section 5.5.1) are displayed graphically by box-and-whisker plots visualizing mean, median, interquartile ranges, SD, and outliers over time: Baseline, last assessment on treatment, and Day-15 follow-up assessment. All subjects with data available at all three time points are included. A corresponding table is included as well.
- Individual absolute change from baseline to last assessment on treatment versus absolute change from baseline to last follow-up assessment is graphically displayed for FEV1, FVC, %FEV1, and %FVC by means of scatterplots with treatment groups color-coded.

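### Spirometry reversibility: subjects enter on a fall of 200 mL or 12%, but count as reversed unless both thresholds are still crossed, so unrecovered falls are reported as reversible

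*SAP*

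**What the plan says.** Section 5.5.13.1 sets the entry rule: "In the subset of subjects experiencing a decrease of" at least 200 mL or at least 12% in FEV1 (or FVC), from baseline to the last on-treatment assessment. The condition is Reversible if no decrease of ≥ 200 mL and ≥ 12% "in FEV1 (or FVC) from baseline is present at the last follow-up assessment". Otherwise it is Not reversible: "If the last follow-up assessment is not fulfilling the above described reversibility criteria, the condition is considered" Not reversible. Subjects without a follow-up assessment are treated as missing.

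The same section lists assessment-level flags ("Assessments meeting the following conditions are flagged in the ADaM dataset"). For FEV1 and for FVC, one flag is change ≤ −200 mL or percent change ≤ −12%. Another is change > −200 mL and percent change > −12%. The Reversible sentence refers to neither.

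Section 9.10.6 repeats the "or" entry rule and says that "the number and percentage of subjects with the condition reversed, not reversed, or missing data on reversibility at the last follow-up result is provided". It does not restate what reversed means. The follow-up value is defined in section 5.5.1: "Last follow-up assessment: Last assessment between EOT + 8 and EOT + 37 days". Section 4.3 explains that follow-up for these endpoints was limited to the safety follow-up period to "allow the assessment of the reversibility of the effects on these endpoints" before other disease-modifying therapies are started.

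**The concern.** A reversibility rule should ask whether the condition that brought the subject into the subset is still present. Here the condition is either threshold crossed, so it has gone only when neither is crossed. The text instead declares it gone as soon as one of the two is not crossed. A subject who entered on a single threshold can therefore be counted as reversed with no recovery, or after getting worse.

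The table is reported by arm as counts and percentages, on an organ system that the SAP lists among its adverse events of special interest. The error favours the reassuring answer.

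**Working it through.** **Inputs.** The thresholds (200 mL, 12%) and the connectives come from section 5.5.13.1. Baseline lung function and the size of the fall are not given in the SAP, so they are assumed below and shown as ranges. The SAP states no figure to reproduce.

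**1. The rules.** Let d be the decrease from baseline b, A the event d ≥ 200 mL, and B the event d/b ≥ 12%.
- Entry, last on-treatment value: A or B.
- Reversible as written, last follow-up value: not (A and B), which is the same as not A or not B.
- Complement of entry: not A and not B, i.e. d < 200 mL and d/b < 12%. This is the second flag.

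Anyone meeting the complement also meets the written rule, but not the reverse. The two differ exactly for subjects who cross one threshold and not the other at follow-up.

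**2. Where they differ.** The thresholds coincide only at b = 200/0.12 = 1,667 mL. Above that, an unchanged fall from 200 mL up to, but not including, 0.12 × b enters the subset and is called reversible. Below it, the range runs from 0.12 × b up to 200 mL.

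| Baseline | 12% of baseline | Unchanged falls called reversible |
|---|---|---|
| 1.4 L | 168 mL | 168 to < 200 mL |
| 2.0 L | 240 mL | 200 to < 240 mL |
| 3.0 L | 360 mL | 200 to < 360 mL |
| 3.5 L | 420 mL | 200 to < 420 mL |
| 4.0 L | 480 mL | 200 to < 480 mL |

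**3. Individual cases.**

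| Baseline | On treatment | Follow-up | As written | Complement of entry |
|---|---|---|---|---|
| 3.2 L | 300 mL (9.4%) | 300 mL (9.4%) | Reversible | Not reversible |
| 3.5 L | 210 mL (6.0%) | 410 mL (11.7%) | Reversible | Not reversible |
| 4.0 L | 500 mL (12.5%) | 470 mL (11.8%) | Reversible | Not reversible |
| 4.0 L | 300 mL (7.5%) | 100 mL (2.5%) | Reversible | Reversible |

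The second subject has worsened. The fourth has recovered, and both rules agree.

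**4. Size across a population (assumed inputs).** Baseline is normal with mean 2.8–3.6 L and SD 0.6 L. The on-treatment fall is normal with mean 150–350 mL and SD 250 mL. There were 1,000,000 simulated subjects per scenario, each recovering the same fraction of the fall by follow-up. Results are among those who enter:
- No recovery: 28% (2.8 L, 350 mL) to 67% (3.6 L, 150 mL) are reversible as written. The complement gives 0%.
- 50% recovery: the written rule exceeds the complement by 30 to 53 percentage points.
- 80% recovery: the excess is under 1 percentage point.

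A second set of assumptions (mean baseline 3.0–3.8 L, mean fall 100–300 mL, SD of the fall 200–300 mL) gives 33–83% at no recovery.

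**The case against.** The best reply is that the sentence was meant as neither a 200 mL nor a 12% decrease remaining. The flags support this: the second is the exact complement of the first, and since it is not a low value it has little other use in the planned tables. That is good evidence of intent. But the Reversible sentence does not cite the flag, it changes connective from the entry clause, and section 9.10.6 supplies no definition that would correct it. Coded as written, it gives the wrong classification. If intent and text differ, the text needs changing.

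The second reply is that little rests on this count. The output is descriptive, with no test or alpha, and the rule is the same in both arms. Section 9.10.6 also plans summaries of change by visit, box plots, and scatterplots of each subject's change to last on-treatment against change to last follow-up, and results are listed. Unrecovered subjects would be visible there. This stands as a limit on the consequence, but those displays do not correct the stated percentage reversed.

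The third reply is that the zero-recovery figures are a stress case. That is right: the effect runs from negligible to large depending on a recovery rate that the SAP does not give, and it should be quoted across that range.

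**Conclusion.** The concern holds. As written, the Reversible criterion is not the complement of the entry criterion, and subjects with an unchanged or larger fall can be reported as reversed. This follows from the wording and needs no assumption. The error runs one way, towards a higher reversible proportion. Only subjects still crossing exactly one threshold at follow-up are misclassified; those crossing both are correctly Not reversible.

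The size depends on assumed lung-function distributions and on the recovery rate. The bias is small when recovery is nearly complete and large when it is partial or absent, which is where the table is most needed. Efficacy, alpha and the analysis sets are untouched, so the weight is that of a wrong definition in a descriptive safety table.

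**What to change.** In section 5.5.13.1, define Reversible by the existing flag: at the last follow-up assessment, absolute change from baseline > −200 mL and percent change from baseline > −12%. Any other subject with a follow-up value is Not reversible, and those without one stay missing. Apply this separately to FEV1 and FVC, and state the same criterion in section 9.10.6. With this rule no subject with an unchanged fall can be called reversible at any baseline.

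The cost is one sentence in each section and one line of code, using a flag that is already derived. No new data are needed. The reported reversible proportion may be lower.

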5.5.13.2 Pulmonary function tests - DL_{CO}

DL_{CO} will be assessed in a subset of 333 subjects at selected sites with appropriate and established PFT expertise. DL_{CO} test results are reviewed by a centralized independent reader.

An assessment usually consists of multiple maneuvers. Among multiple maneuvers (reported within the same visit and assessment date), the mean value of the two highest DL_{CO} measurements are derived to represent the DL_{CO} at that assessment. If only one

DL_{CO} measurements is available at an assessment, that measurement is used. Within the eCRF, DL_{CO} values are converted into ‘mmol/min/kPA’ which is the unit used in reporting.

In addition, DL_{CO} based on acceptable results only is derived, for sensitivity analyses. A maneuver is considered acceptable if ERT’s overall statement is entered as “OK”, i.e., only assessments reported as “acceptable DL_{CO} data received” or “borderline acceptable DL_{CO} data received” are considered for analysis. The mean value of the two highest acceptable DL_{CO} measurements is derived. If only one acceptable DL_{CO} measurements is available at an assessment, that measurement is used.

Only these derived assessment-level values are used for any further derivation, the term ‘DL_{CO} at visit’ will refer to this value derived from the individual maneuver measurements.

The following derivations are performed (for DL_{CO} from all measurements and DL_{CO} from acceptable measurements separately):

- DL_{CO} adjusted for Hemoglobin (Hb) is derived based on the method of Cotes [[Macintyre 2005](#)] using the Hb reported by the central laboratory (or from local laboratory if missing) at the same nominal visit based on below formulae:
 - $DL_{CO\ Hb\ corrected} = DL_{CO} \times (10.22 + Hb\ [g/dL]) / (1.7 \times Hb\ [g/dL])$ for male subjects older than 14 years;
 - $DL_{CO\ Hb\ corrected} = DL_{CO} \times (9.38 + Hb\ [g/dL]) / (1.7 \times Hb\ [g/dL])$ for female subject subjects and all subjects ≤ 14 years;

If no Hb value is available at the corresponding visit, this variable is missing.

- Predicted DL_{CO} corresponding to each assessment is derived based on Cotes [[Cotes 1993](#)] as follows:
 - $DL_{CO\ predicted} = 11.11 \times Height\ [m] - 0.066 \times Age\ [years] - 6.03$
for male subjects, age is set to 25 years if age below 25 years;
 - $DL_{CO\ predicted} = 8.18 \times Height\ [m] - 0.049 \times Age\ [years] - 2.74$
for female subjects, age is set to 25 years if age below 25 years;

The age used in above formula is derived as follows: Age at baseline + 0.5 + (Date of assessment – Date of (re-)screening) / 365.25;

- Percent Predicted DL_{CO} is derived as:
 $100 \times DL_{CO\ Hb\ corrected} / DL_{CO\ predicted}$

Baseline is flagged and absolute and percent changes from baseline are calculated for each post-baseline value, and last on-treatment and follow-up assessments are derived, as described in Section 5.5.1.

Assessments meeting the following conditions are flagged in the ADaM dataset:

- Percent change from baseline in DL_{CO}: < -20 %
- Percent change from baseline in hemoglobin corrected DL_{CO}: < -20 %
- Absolute change from baseline in percent predicted DL_{CO}: < -20 %

